1 PROJECT TITLE

A randomised controlled trial of cognitive behaviour therapy and motivational interviewing for people with Type 1 diabetes mellitus with persistent sub-optimal glycaemic control.

PLANNED INVESTIGATION

1. Objectives

1.1 We will use a three armed randomised controlled trial to test the effectiveness of cognitive behaviour therapy compared to motivational interviewing and usual care in helping patients with Type 1 diabetes improve their glycaemic control.

1.2 To examine the cost effectiveness of motivational interviewing and of cognitive

behaviour therapy compared to usual care for improving glycaemic control.

1.3 To identify cognitive, behavioural and biological predictors of outcome.

2. Existing research

2.1 Clinical features of Type 1 diabetes

Type 1 diabetes (T1DM) is a chronic condition characterised by an absolute deficiency of insulin with an onset usually in childhood and early adulthood. Management requires the patient to self-administer insulin injections several times a day and adhere to diabetes specific dietary, exercise and self monitoring regimens. The aim is to achieve blood glucose levels to near as normal, as persistent hyperglycaemia and duration of diabetes increase the risk of developing diabetic complications (nephropathy, neuropathy and retinopathy) and early death. While well-controlled diabetes is not disabling complications early in life can be handicapping. Adherence to diabetes self care regimen is a critical factor contributing to poor glycaemic control.

2.2 Epidemiology

The prevalence of T1DM is around 3 per 10,000 per year and is rising.^{1,2} The mortality rates are still unacceptably high especially in the young, women, materially deprived groups and ethnic minorities. In South Tees T1DM is associated with a 6- and 3-fold increase in all cause standardised mortality in women and men respectively compared to the local population³ and material deprivation was associated with a doubling of mortality.³ Individuals with T1DM from ethnic minority groups have a 2- fold increase in mortality.⁴ Diabetes and its complications constitute around 5% of the National Health Service (NHS) budget.⁵ Intensive medical regimens and strict control of blood glucose can reduce the rate of complications⁶ but are costly⁷ and improvements are not always sustained when the intensive regimen ends.⁸

2.3 Psychological factors associated with sub-optimal glycaemic control

Depressive disorders are more common in adolescents⁹ and adults with T1DM than healthy controls.¹⁰ In a recent meta-analysis, depression was associated with hyperglycaemia with a mild to moderate effect size.¹¹ Expressed emotion and family conflicts appear to be associated with poor control in prospective studies.¹² Eating disorders can be twice as common in women with T1DM than matched controls¹³ and associated with a 3-fold risk for retinopathy.¹⁴ In adolescence, there is often a worsening of glycaemic control¹⁵ due to intense physiological¹⁶ and psychological changes which may lead to reduced self-care, onset of eating problems and initiation of substance misuse. While some adolescents do overcome the turbulence, for a significant proportion adherence difficulties continue into adulthood.

2.4 Reviews of randomised controlled trials

Education and psychological interventions are the two most common non-pharmacological interventions studied in people with T1DM. They are often grouped together or described as 'psychosocial' but are different clinical specialities. Educational interventions are based on principles of learning that provide information, instruction, advice and support. On the other hand, psychological interventions aim to alter unhelpful affects, cognitions and/or behaviours using principles of psychotherapy, utilising the therapeutic alliance to facilitate change. Psychological services attached to diabetes teams are few and sporadic.¹⁷

Two well-conducted and inclusive reviews of educational and psychosocial interventions for adults¹⁸ and adolescents¹⁹ have concluded that psychological interventions may be effective but serious methodological flaws in individual studies limit their interpretation. A recent thorough systematic review and meta-analysis of controlled studies of behavioural interventions in adolescents with T1DM identified 24 randomised controlled trials (RCT) of educational or psychosocial interventions.²⁰ They reported a mean effect size of 0.3 for psychosocial and glycaemic control outcomes when only the RCTs were pooled. This effect size is equivalent to a modest 0.6% improvement in glycosylated haemoglobin (HbA_{1c}). Theoretically based interventions were more effective. There were some limitations to this analysis. First, educational and psychological interventions that may be different clinical disciplines were pooled together which may have increased the heterogeneity of the pooled sample. Second, the results of the meta-analysis may be limited as control groups for two studies^{21,22} were used twice in the same analysis. Third, the HbA_{1c} values of one study was not used to calculate the pooled effect size.²³ Fourth, as the object of the review was limited to adolescents with T1DM, the results could not be generalised to an adult population with T1DM.

We carried out an independent systematic review of RCTs of psychological interventions for improving glycaemic control in patients with diabetes based on a Cochrane Collaboration protocol.²⁴ We limited our review to RCTs as these are the most rigorous we wish to compare ours with. We excluded interventions that were based on education theory. We included adults and adolescents. We identified 11 RCTs in people withT1DM. The interventions that were being tested included social learning;²⁵ multi-family group therapy;²² problem solving²⁶ and self-management training²⁷ in families where patient and parents are seen in separate groups; family therapy;^{23,28} patient empowerment;²⁹ problem solving in individuals;³⁰ cognitive analytic therapy; ³¹ relaxation therapy;³² and stress management.³³ When these studies were pooled we derived an effect size of 0.1 (95% confidence interval -0.7 to 0.9) for improvement in HbA_{1c}. We used a random effects model as there was evidence of significant heterogeneity in the fixed effect model (Q=15.16, p=0.02). We could not conclude from our meta-analysis that the psychological models are effective in improving glycaemic control, although the upper limit of the confidence interval suggests that they could potentially be very effective.

2.5 Limitations of previous studies

Few studies were based on representative samples of people with T1DM. Three studies defined the clinic population from which eligible patients were sampled, such as incident cases²³ or screening clinic lists.^{28,31} Most studies used convenience sampling such as advertisements,²⁶ referrals from clinics^{22,27} or gave insufficient detail.^{30,32,33} Convenience sampling would result in recruiting patients and families motivated to change and more likely to improve. Patients who were having difficulties with their diabetes self-care but not in a state of readiness to change would be excluded.

Most studies did not recruit people from ethnic minorities despite being based in ethnically diverse settings. Most studies involved young children and adolescents.^{22,23,25-27,33} Young adults have new difficulties and transitions, such as education, careers, intimate relationships and planning families. None of the RCTs in adults with T1DM³⁰⁻³² addressed the role of life events and chronic social difficulties on a person's ability to manage his/her diabetes. The majority of studies were grouped based. This may be due to the cost of medical insurance in the US, where most of the studies were conducted. While groups may have the advantage of sharing experiences they do not allow for individualised treatments and may deter patients who are more introverted or who are psychologically distressed.

None of the studies described the method of randomisation or allocation concealment or whether outcome assessors were blind to allocation status. The sample sizes tended to be small. No study described a power calculation or conducted an intention to treat analysis.

2.6 Implications of previous research for proposed study

Sub-optimal control in T1DM is common and associated with increased morbidity and mortality. There have been a broad range of psychological interventions to help people improve their glycaemic control but the quality of these are generally poor and few have used evidence-

based theoretical models. Those studies based on a cognitive behavioural model appear to be most effective. There were no studies which compared brief interventions such as motivational interviewing with longer interventions such as cognitive behaviour therapy. Such comparisons would allow differences in cost effectiveness, applicability in busy clinical settings, patient's resistance to change and patient acceptability to be examined. We propose two interventions based on different theoretical models.

2.7 A motivation model of understanding adherence

Motivational interviewing (MI) is based on a widely used model of health behaviour change which states that two components need to be addressed for sustained behaviour change; first a recognition of the importance of a problem, or conviction that change is needed and second the degree of self-efficacy which reflects confidence in one's ability to bring about a particular behaviour change successfully.³⁴ In contrast to conventional medical models where the health professional is the expert and the patient the passive recipient of education and advice, MI elicits the patient's concerns as the expert on his difficulties.

MI was originally developed in addictions where its effectiveness has been widely documented.³⁵⁻³⁸ It has since been applied to a broad range of health problems, such as eating disorders³⁹ hypertension in primary care⁴⁰ and smokers.⁴¹ There is emerging evidence that it may be effective in improving adherence and glycaemic control in an obese Type 2 female population.⁴²

The advantages of MI is that it can be delivered as a brief manual based intervention for a busy clinical setting using computerised tools and non mental health professionals can be trained in its use.⁴³

2.8 A cognitive behavioural model of understanding adherence

Cognitive behaviour therapy (CBT) is a pragmatic approach to managing symptoms or illnesses which involves enabling patients to change aspects of their behaviour and the way they think to bring about physiological changes.^{44,45} This model is widely used in the treatment of anxiety disorders and referred to as Lang's three systems model⁴⁴. It is based on psycho-physiological evidence that current physiological, behavioural and cognitive responses operate largely in synchrony with one another. Changing one response system such as the person's behaviour will bring about changes in the other two response systems. In diabetes, enabling patients to make cognitive and behavioural changes to their self-care could improve their glycaemic control. For example fears about having a hypoglycaemic attack and perceptions about degree of control over it (cognition) lead to avoiding appropriate diabetes self care (behaviour) which leads to poor diabetic control (physiological).⁴⁶ Fearful cognitive responses to previous hypoglycaemic attacks and may be reactivated during times of stress.

While Lang's model focuses on the here and now, Beck's model of emotion, (depression and anxiety), incorporates a developmental perspective. The cognitive theory of emotion stresses that particular biases in information-processing will lead to congruent emotions.^{47,48} These biases are reported to be linked to early life experiences which form personal schema, basic attitudes or assumptions and core beliefs. At times of stress, negative thoughts, such as those related to diabetes, might also be activated which then influence coping behaviour. These two models will be used to devise a coherent developmental formulation of the patient's problems which will guide the use of appropriate of cognitive behavioural interventions.

2.9 Summary

Evidence for the effectiveness of psychological interventions to improve diabetes self-care and glycaemic control is poor. We have described two different theoretically based psychological models which have the common goal of improving diabetes self-care. We propose to test the effectiveness of these models in an inner city sample representative of the ethnic and socioeconomic diversity of people with T1DM.

3: Research methods

3.1 Hypotheses

Main hypothesis: Motivational Interviewing (MI) plus Cognitive Behaviour Therapy (CBT) will be more effective than usual care at improving glycaemic control in T1DM at 12 months follow up.

Subsidiary hypotheses

(i) Motivational interviewing will be more effective than usual care at improving glycaemic control at 12 months follow up.

(ii) MI plus CBT will be more effective than MI alone at improving glycaemic control at 12 months follow up.

3.2 Design

The design we have chosen is the gold standard for evaluating treatment efficacy; a randomised controlled trial with three arms, MI, MI plus CBT and usual care (see figure 1 – Version 2 dated 18.08.03).

3.3 Setting

Participants from five hospital trusts in South London (King's College, Guy's and St Thomas', Lewisham, Queen Elizabeth (Woolwich) and Mayday) and three hospital trusts in Manchester (North Manchester General Hospital, Manchester Royal Infirmary, Stockport General Hospital) will be recruited. Lambeth Southwark and Lewisham boroughs are one of the most ethnically diverse⁴⁹ and socio-economically disadvantaged⁵⁰ populations.

3.4 Eligible population

Each diabetes clinic has its own patient database. All current records include patient's age, sex, ethnicity, date of diagnosis, type of diabetes, medication, HbA_{1c} past and present. Each of these databases will be searched to identify patients who have T1DM. Patients who have not had an HbA_{1c} recorded in the previous 12 months will also be included as non-attenders are a vulnerable group.

3.5 Case definition

Diabetes mellitus will be defined according to World Health Organisation criteria.⁵¹ T1DM will be defined: a) onset before age 35 years b) requiring insulin within 6 months from onset and/or c) ketonuria. Sub-optimal glycaemic control will be defined as having at least one HbA_{1c} result between 8.2 and 12% in the previous 12 months. The minimum duration of diabetes will be 2 years to avoid the honeymoon period. We have selected the lower limit of 8.2% as the Diabetes Control and Complications Trial suggests that optimal glycaemic control is a HbA1c of around 7.2% with a significant increase in the risk of complications for every 1% rise in HbA1c above this level.⁶ Our upper limit of 12% was selected to exclude a small proportion of patients who are likely to be very physically ill and at risk of being admitted as an emergency. Throughout the study, all measures of HbA1c will be standardised according to the DCCT criteria⁶.

3.6 Screening procedure

The diabetes consultants will identify suitable patients and invite them to learn more about the study. Upon on their agreement, the research co-ordinator will contact the patients to discuss the trial in more detail. Interested participants will be sent an appointment with the research co-ordinator at their local hospital to obtain informed consent and then to assess whether the patient meets trial criteria.

3.7 Planned trial criteria

Inclusion criteria: 1) Age 18 to 65; 2) Fluent in English; 3) Not in any other trial 4) A stable dose of antidepressants for 2 months; 5) current HbA_{1c} between 8.2 and 12%.

Exclusion criteria: 1) Pregnancy (if a participant does become pregnant during the study she will remain in the study unless there is a medical contra-indication); 2) Acute/serious medical illness after discussion with the patients physician; 3) severe end stage diabetes complications, that is, registered blind, severe renal disease (creatinine greater than 300 mmol/l); 4) Severe mental disorders; manic-depression, psychotic illnesses, alcohol dependence, learning disability.

3.8 Baseline measures

Socio-demographic: data will be collected on age, sex, level of education, occupation, marital status, self report ethnicity.

Biological: HbA_{1c} (measured at screening); duration of diabetes; complications - retinopathy will be measured by retinal photography;⁵² neuropathy will be measured using the vibration-perception threshold⁵³ and nephropathy will be measured using an early morning urine sample for albumin-creatinine ratio.⁵⁴ Body mass index and blood pressure will be measured.

Diabetes specific cognitions: The *Diabetes Specific Health Beliefs-Experience of Treatment and Benefit Barriers* subscale for insulin treated diabetes will be used to measure the patient's perspective of adherence to the diabetes regimen.⁵⁵ *Fear of Hypoglycaemia* questionnaire⁴⁶ will be used as worries are not adequately measured by the *Diabetes Specific Health Beliefs*. The Beliefs about Medicine Questionnaire will be used to elicit beliefs about the use of insulin.⁶⁷

Diabetes specific behaviour: The *Summary of Diabetes Self –Care Activities* questionnaire measures frequency of adherence to eating habits, exercise levels, glucose monitoring and medication.⁵⁶

Psychiatric morbidity: This will be measured using the *Primary Care Evaluation of Mental Disorders (PRIME-MD PHQ)*⁵⁷ which is a self report measure for depressive, anxiety, alcohol, somatoform and eating disorders and using the *General Health Questionnaire-12*.⁶⁸ The *Life Events Questionnaire*⁶⁹ will be used to determine perceived stress and the World Health Organisation's *Alcohol Use Disorders Identification Test* to measure alcohol consumption.⁷⁰

Quality of life: The *Short Form-36* ⁵⁸ will be used which has been used extensively in diabetes. The *EuroQOL*⁷¹ will be used in order to conduct a cost-utility analysis, and the *Diabetes Quality of Life* measure to look at diabetes-specific themes. ⁷²

Costs: *Client Services Receipt Inventory*⁵⁹ gives a detailed description of service use patterns, medication (including insulin), employment and household family responsibilities in the previous 3 months.

Social support: from family, friends and health professionals will be examined by the *Significant* Others Scale.⁶⁶

3.9 Randomisation procedure

Before randomisation all participants will receive a 2 page fact sheet on Type 1 diabetes to ensure that the minimum acceptable level of diabetes education is equal in all three groups (see factsheet version 1 - 18.08.03). Randomisation will be conducted by the Clinical Trials Unit (CTU) at the Institute of Psychiatry who will prepare a randomisation list using permuted blocks of random sizes to ensure an equal number of patients in each group while avoiding possible predictability associated with blocks of fixed sizes. Allocation concealment will be ensured by the randomisation list being held by the CTU who will use a program that reveals the allocations only when the patient identification number is entered.

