3.15 Proposed sample size

We will assume that the baseline HbA_{1c} is approximately 9.0% ⁶. We will assume that the post CBT or post MI mean will be 8% based on the evidence that a reduction of 1% in HbA_{1c} is associated with a clinically and statistically significant reduction in risk of developing diabetes complications.⁶ We will assume that control mean HbA_{1c} will be 8.8% (based on the principle that participating in the study as a control can have a slight improvement on glycaemic control.⁶ We further assume that the standard deviation of the changes is approximately equal to 1.65 based on the average standard deviation of the change scores in a RCT of cognitive analytic therapy at 3 month follow up from end of intervention period.³¹ We therefore require 90 subjects per group to achieve 90% power to detect the difference in mean change between two groups using a t-test with a 5% level of significance. Allowing for a 20% drop-out rate, we therefore need 113 subjects for each arm giving a total of 339 participants.

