3.16 Statistical analysis

Data will be entered using SPSS and analysed using STATA. The success of randomisation will be assessed by comparing baseline characteristics. The difference in mean reduction of HbA_{1c} between the CBT, MI and control groups will be estimated using a linear mixed model incorporating fixed effects of group, time and group by time and a random effect for subjects. All available data will contribute to the analysis including data on subjects who dropped out or withdrew from the trial (intention to treat analysis). The same analysis will be used to identify other predictors, such as presence of diabetes complications and psychiatric morbidity and effect modifiers such as social support. Secondary outcomes (illness perceptions and diabetes specific behaviours) will be analysed using linear mixed models and generalised linear mixed models for dichotomous outcomes. We will model the change in mean HbA1c over time using a linear trend and a quadratic one if needed. The change over time is reflected by the linear trend, "the effect of time", and a treatment effect would correspond to a group by time interaction. A comparison of participants and non-participants of the RCT will be performed on socio-demographic data available from the databases. A comparison of the baseline characteristics of completers and non completers will be done. Economic analysis: Total average costs will be linked with the main outcome (improvement in HbA_{1c}) for each group in the form of a cost-effectiveness analysis. A cost-utility analysis will be conducted on the SF-36. This will offer a simpler decision rule and allow explorations of cost per quality-adjusted life-year (QALY) gained.

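### The randomisation list as described balances total group sizes but not trusts, and the model has no trust term, so chance imbalance in HbA1c change by trust is neither prevented nor adjusted for (a small loss of precision)

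*Protocol*

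**What the plan says.** Section 3.9 gives the trials unit the task to "prepare a randomisation list using permuted blocks of random sizes to ensure an equal number of patients in each group". It speaks of one list throughout: "Allocation concealment will be ensured by the randomisation list being held by the CTU", whose program releases an allocation on entry of the patient's identification number. No trust, city or other stratum is named as an input.

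Section 3.3 describes the sites: "Participants from five hospital trusts in South London" and "three hospital trusts in Manchester", so eight trusts in two cities.

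Section 3.16 lists the terms of the primary model as "incorporating fixed effects of group, time and group by time and a random effect for subjects", and adds that "a treatment effect would correspond to a group by time interaction". Trust does not appear among these terms, nor among the examples of other predictors and effect modifiers in the same section.

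Usual care (section 3.10, control group) is a shared minimum: an annual review with a common HbA1c target.

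**The concern.** Blocking on a single list keeps the three totals close to each other. It does nothing for the split between arms inside a trust, because consecutive places on the list go to whichever trust enrols next. Agreed usual care is a floor, so care above that floor, and with it the course of HbA1c over 12 months, may differ between trusts. If one arm happens to draw more patients from trusts where HbA1c is falling anyway, part of the between-arm difference reflects trust. The stated model has no term that would remove it.

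What is at stake is precision, together with the awkwardness of a late argument about centre adjustment if, say, Manchester turns out to be unevenly spread across arms.

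**Working it through.** **1. The plan's own figure.** Section 3.15 says "We will assume that the post CBT or post MI mean will be 8" per cent. It sets the control mean at 8.8%, the SD of change at 1.65, power at 90% and the level at 5%.
- Difference: 8.8 − 8.0 = 0.8.
- n per group = 2 × (1.960 + 1.282)² × 1.65² / 0.8² = 89.4, rounded up to 90.
- With 20% drop-out: 90 / 0.8 = 112.5, so 113; 3 × 113 = 339.

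The stated figures reproduce with a two-sided test. Power at 90 per group is 90.2% by the normal formula and 89.9% by the t-test.

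**2. How uneven can the arms be by trust?** Simulation of one list for 339 patients. Assumptions: eight equal trusts and block sizes of 3, 6 and 9, neither given in the protocol. Each trust has about 339 / 8 = 42 patients, or 14 per arm.
- The largest difference between two given arms in any trust has a median of 8 or 9 patients, depending on the run. It is 8 or more in about 65% of lists.
- The Manchester share differs between two given arms by a median of about 4 percentage points, and by 10 points or more in 11% to 12% of lists.
- With unequal trusts (322, 208 and 94 from section 3.18, the other five assumed at 80 each) the results are similar: median 8 patients, and about 4 points for Manchester.

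The first figure is the worst of eight trusts, so it overstates the effect on the estimate. Step 3 gives that effect.

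**3. How far does this move the treatment difference?** Let ρ be the share of the variance of HbA1c change that lies between trusts. The protocol gives no value, so 2% to 10% is assumed. With 113 per arm and eight equal trusts:

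SD of shift = 1.65 × √ρ × √(8 × 2 × (1/8) × (7/8) / 113) = 0.205 × √ρ

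| ρ | SD of shift (HbA1c points) |
|---|---|
| 0.02 | 0.03 |
| 0.05 | 0.05 |
| 0.10 | 0.06 |

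Simulation agrees to within 0.01. For comparison, the standard error of the difference is 1.65 × √(2/113) = 0.22, or 1.65 × √(2/90) = 0.25 with 90 per arm, and the target difference is 0.8. In simulation without a trust term, the type I error was 4.8% (ρ = 0.05) and 5.6% (ρ = 0.10), with power about 90%.

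**4. What would be gained?** Removing the trust share leaves SD = 1.65 × √(1 − ρ). Two-sample t power at 90 per group, difference 0.8:

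| ρ | SD | Power |
|---|---|---|
| 0 | 1.650 | 89.9% |
| 0.02 | 1.633 | 90.5% |
| 0.05 | 1.608 | 91.3% |
| 0.10 | 1.565 | 92.7% |

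The gain is 0.6 to 2.8 points. A simulation with separate lists per trust plus adjustment gave about 91% to 92.5% over the same range.

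**5. Which model term does the work?** The treatment effect is the group-by-time interaction, with a random effect per subject. In simulated data (two arms of 113, five visits, trusts differing in level and in change), adding trust as a main effect left the interaction estimate and its standard error unchanged to four decimals when data were complete (for example −0.9703, SE 0.1963, with and without trust). With drop-out it moved the estimate by less than 0.01. Trust by time did move the estimate, although in a single data set the standard error need not fall (0.1767 became 0.1787 in one).

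**The case against.** The strongest reply is that central blocked randomisation without stratification is a valid design. Chance imbalance is already allowed for in the standard error, and the gain is at most about 3 power points under variance shares that no document supports. That stands, and it sets the size of this point.

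A reader might infer more than the protocol supports:
- *That the comparison is biased by centre.* It is not. The imbalance is random and the type I error stays near 5%.
- *That all variation between trusts remains in the error.* Stable differences in HbA1c level go largely into the subject effect. Only differences in change over time matter.
- *That the list is declared unstratified.* Section 3.9 never says so. A single list with the patient number as the only named input is the natural reading, but it is an inference. Stratification might be set out in a trials-unit specification or an analysis plan that is not at hand. Even so, sections 3.9 and 3.16 state a method and a set of model terms, and neither includes trust.
- *That usual care is uncontrolled.* All centres share an HbA1c target and refer to a usual-care protocol, and section 3.5 standardises HbA1c measurement. This narrows the likely differences between trusts without removing them.

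The appendix also suggests that the trial was under way when it was written (a change of eligibility range approved in 2004 and a 9-month extension). The change to the list may therefore come too late.

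**Conclusion.** The point holds as a low-cost improvement in precision and clarity. With eight trusts in two cities, nothing stated in the protocol balances the arms by trust or adjusts for differences between trusts in HbA1c change. The expected benefit is about 0.5 to 3 power points if trust accounts for 2% to 10% of the variance in change, and close to nothing if it accounts for less. That range, the block sizes and the trust sizes are assumptions. The planned 90 per group, 113 per arm and 339 in total need no change, and results from the plan as written would still be valid.

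**What to change.** In section 3.9, state that the trials unit prepares a separate random-block list for each trust, or at least for each city if some trusts are expected to enrol few patients. The trust is then entered together with the patient number before the allocation is released.

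In section 3.16, pre-specify trust and trust by time as fixed effects. Alternatively, include trust in a baseline-adjusted comparison of HbA1c at 12 months. A trust main effect alone in the present model is not enough (step 5 of the working).

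If randomisation has already begun, leave the list as it is and change only the model, before outcome data by arm are seen.

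Cost: one setting in the allocation program, at most one incomplete block per stratum, and 7 + 7 = 14 degrees of freedom with a linear time trend (7 in the baseline-adjusted 12-month comparison). With 339 patients this is affordable.
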